## INVESTIGATOR STUDY PLAN - REQUIRED

*Symptom Identification Scale – 24 (BASIS-24)*, a 24-item measure of psychiatric and substance-related symptoms and level of functioning.

Given the limited scope of the proposed study and the resulting proposed sample size, we will collect only preliminary data on **mechanisms of change** and conduct exploratory analyses of these potential mechanisms. We identified potential mechanisms from published studies of *Seeking Safety*, the alcohol treatment literature, and Deaf mental health literature. Potential mediators are participants' reported ability to use coping skills, practice self-compassion, and understand health information. Potential moderators are motivation for treatment and participant-reported provider cultural competency. These constructs will be measured by the *Coping Self-Efficacy Scale*, a 26-item measure of perceived ability to cope with past-month challenges; the *Self-Compassion Scale – Short Form*, a 12-item measure of self-compassion in instances of perceived failure, inadequacy, or suffering; the *Ask, Understand, Remember Assessment (AURA)*, a 4-item measure of one's ability to obtain, understand, and remember health information communicated by a provider; the *Stages of Change Readiness and Treatment Eagerness Scale (SOCRATES 8A)*, a 19-item measure assessing readiness for change among individuals with AUD; and *Patient-Reported Healthcare Provider Cultural Competency*, a 9-item measure rating a provider's ability to interact with patients from one's cultural group.

**Exit Interview (optional).** After a participant's participation in the study is complete, they will be given the option to participate in a videophone exit interview. This interview will be conducted by an ASL-fluent interviewer. The participants will be asked their opinions about how the current study was designed and if any improvements can be made for future research studies (see *Signs of Safety* Exit Interview questions attached). For example, participants will be asked questions about their experience of participating in the research study, including logistics, accessibility, communication, and technology. The exit interview will take approximately 60 minutes. Participants will receive an additional \$50 Visa gift card if they choose to participate in the exit interview.

### 12. DATA AND SPECIMEN BANKING\*

N/A

### 13. Data Analysis and Management\*

Data will be entered into Research Electronic Data Capture (REDCap), a secure web-based data capture application that provides real-time data entry validation (e.g., data types, range checks). UMass Quantitative Methods Core personnel will customize the database to track recruitment, intervention delivery, and outcome assessments. Data will be exported to *SAS* and *ATLAS.ti* for analysis.

Analyses will be conducted as intent-to-treat, with all randomized participants included in the analysis regardless of treatment adherence or missing data in any time points. We will use the mixed procedure (PROC MIXED) in *SAS* to analyze the longitudinal data by fitting the models described below – a procedure that allows for data that are missing at random by including all available data from each participant in the analysis. In the event that a participant has no

## INVESTIGATOR STUDY PLAN - REQUIRED

available outcome data, we will examine their sociodemographic characteristics to compare with those participants who do have available outcome data.

**Analytic plan for feasibility.** For quantitative feasibility outcomes, we will calculate descriptive statistics for the overall sample and separated by treatment arm: mean number of participants screened and enrolled per week; rate of retention; clinician treatment fidelity (rates of integrity, rates of differentiation); participant adherence (number of sessions completed, rates of between-session homework completion); and assessment process (proportion of assessments completed, mean duration of assessment calls). We will compare retention, fidelity, and adherence between the two treatment conditions using chi-square and t-tests.

**Precision of rate estimation:** Based on pilot results, we anticipate at least 45 of the 60 enrolled participants will be retained through immediate post-treatment. See *Section 25. Local Number of Subjects* for more information on the estimated post-attrition sample size and retention rate.

For qualitative feasibility outcomes, open-ended responses to the *End of Session* and *End of Treatment Questionnaires* will be analyzed in *ATLAS.ti* for themes regarding satisfaction with each study arm (e.g., *What comments or suggestions do you have about today's session?*, *How could this treatment be more helpful to you?*). We will use an iterative, grounded theory approach employing two major techniques: (1) content analysis, where the number of similar responses will be tallied and described; and, (2) a summary of the answers to questions outlined by Casey (e.g., *What ideas will be especially useful for the intervention?*).

**Analytic plan for preliminary clinical outcomes.** We will compare treatment arms using two primary clinical outcomes at immediate post-treatment and one-month follow-up: (1) past 30-day alcohol use frequency/quantity (from *Alcohol Timeline Followback*); and, (2) past 30-day PTSD severity (from *PCL-5*). For **alcohol use**, outcome variables are: % drinking days per week (i.e., days with 1+ drink); % binge drinking days per week (i.e., days with 5+ drinks for men, 4+ for women); and mean number of drinks per week. These variables will be calculated from daily data collected with the *Alcohol Timeline Followback* for 30 days (4 weeks) prior to the last drink before baseline assessment, throughout the 12-week intervention or waitlist period, and throughout the one-month follow up period. Such a weekly measure will allow for estimation of changes per weekly intervention session in the experimental condition as compared to waitlist control.

Our initial unadjusted group comparisons at immediate post-treatment/week 12 and at the end of the one-month follow-up period/week 16 will use a standard t-test (or Wilcoxon non-parametric test, depending on the outcome distribution). Below, we describe models for analyzing adjusted group differences and for analyzing the longitudinal data. We acknowledge that, with the small sample size of this feasibility study, the following models may be optimistic in terms of their capability to reliably estimate and to test interactions. However, they will provide insight into possible effect sizes for planning the larger clinical trial.

We will first compare differences in weekly drinking between the two study conditions at pre-, during, and post- intervention periods using mixed effects models (Model 1):

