**Study Conditions.** After enrollment, the Study Assessor will conduct the baseline assessment via videophone. Participants will then be randomly assigned to one of two conditions: (1) *Seeking Safety + Signs of Safety* toolkit, or (2) assessment-only waitlist control. Randomization will occur within each study site and stratified by gender. The Biostatistician will generate a computerized random number series and place numbers in individual sealed opaque envelopes. The RC will open an envelope to randomly assign a treatment condition to the participant. Both the PI and Study Assessor will be blind to study condition. (*Note: the Study Assessor will remain blind to study condition until the end of the post-treatment assessment, at which point she will*

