## INVESTIGATOR STUDY PLAN - REQUIRED

$Y = b0 + b1*int\_pr + b2*fu\_pr + b3*e + b4*int\_pr*e + b5*fu\_pr*e + \text{other predictors (p\_chars, c\_chars, clinician, study site, etc.)} + \text{random effects}$

Where:  $Y$  = alcohol use dependent variable;  $int\_pr$  = 1 for intervention period, = 0 otherwise;  $fu\_pr$  = 1 for follow-up period, = 0 otherwise;  $e$  = 1 for experimental arm, = 0 for control arm;  $p\_chars$  are participant characteristics (e.g, age, gender);  $c\_chars$  are clinician characteristics (e.g, age, gender); clinician indicators will capture differences in clinician approaches; and, study site indicators will capture differences in location of intervention delivery. Random effects (i.e., participants) will account for unmeasured participant characteristics.

We will examine the linear time trend of intervention effects using interrupted time series analysis (Model 2):

$Y = a0 + a1*wk + a2*int\_pr + a3*wk\_aft + a4*e + a5*wk*e + a6*int\_pr*e + a7*wk\_aft*e + \text{other predictors (p\_chars, c\_chars, clinician, study site, etc.)} + \text{random effects}$

Where:  $Y$  = alcohol use dependent variable;  $wk$  = week number starting with 1 for the first week of data collection;  $int\_pr$  = 1 for intervention period, = 0 otherwise;  $wk\_aft$  = # of week after the intervention starts;  $e$  = 1 for experimental arm, = 0 for control arm; and other predictors and random effects as defined in Model 1. Both models will include multilevel clustering to account for repeated measures from the same participant, as well as correlation among participants receiving intervention in the same study site.

For **PTSD symptoms**, the primary outcome is past 30-day total symptom severity on the *PCL-5*. We will compare study conditions on the *PCL-5* total symptom severity score at each time point using a mixed effects model (Model 3). Fixed effects are: study condition (experimental vs. control), time point (four indicator variables with baseline as the reference group), and interaction of study condition and time point. Similar to Models 1 and 2, we will adjust for participant and clinician characteristics; within-clinician, within-site, and repeated measures correlation; and random effects (i.e., unmeasured participant characteristics).

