**Sample size and power calculation:** Our proposed sample size is based on pilot results and the limited scope of the proposed pilot RCT. A clinically significant effect should be used for planning a future full-scale RCT. For example, a clinically significant change score for the *PCL-5* is 10 points, equal to an effect size of 0.47 using a standard deviation of 21.2. Our projected sample size of 22 completers per study arm will have 80% power to detect a large effect size (0.80) comparing two means using a two independent sample t-test for the unadjusted group comparisons. To detect a smaller effect size (e.g., clinically significant effect size of 0.47), a larger sample size would be needed, but is not feasible due to the scope of the proposed pilot RCT. We used the unadjusted t-test for the power calculations due to the largely unknown assumptions required to calculate the power for a mixed effects model; however, the mixed effects models will have more power than the unadjusted t-test due to the partitioning of the variance among the various components.

**Analytic plan for potential mechanisms of change.** We will examine potential moderators and mediators of intervention effects. We will compare the two treatment arms on these variables at

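### The week-12 and week-16 arm comparisons ignore the randomization strata, and the adjusted models do not clearly commit to site and gender at randomization for both arms

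*Combined protocol and SAP*

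**What the plan says.** **Design.** Section 11, Study Conditions: "Randomization will occur within each study site and stratified by gender". On sequence generation the plan says only: "The Biostatistician will generate a computerized random number series and place numbers in individual sealed opaque envelopes". No block size or other balancing method is given.

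**First comparison.** Section 13, analytic plan for preliminary clinical outcomes, begins with "Our initial unadjusted group comparisons at immediate post-treatment/week 12" and the end of follow-up at week 16. The test is a two-sample t-test, or a Wilcoxon test if the distribution calls for it. Neither site nor gender enters.

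**Adjusted models.** The same paragraph continues: "Below, we describe models for analyzing adjusted group differences and for analyzing the longitudinal data". Models 1 and 2 (alcohol) allow for participant characteristics, with age and gender as examples, and for study site. Site is explained thus: "study site indicators will capture differences in location of intervention delivery". Clustering is described among participants who receive intervention at the same site. Model 3 (PCL-5) has arm, time point and their interaction as fixed effects. It compares the arms at every time point, adjusting for unnamed participant and clinician characteristics and for within-site correlation.

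**Power.** Section 13, sample size: "We used the unadjusted t-test for the power calculations", with 22 completers per arm, an effect size of 0.80 and a stated power of 80%.

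**The concern.** When randomization is balanced within strata, differences between strata can no longer contribute much to the difference between arms. An unadjusted test still counts that between-stratum variation in its standard error. If site or gender predicts drinking or PCL-5 score, the standard error is then too large, p-values and intervals are wider than the design warrants, and precision is lost in a trial expecting only 45 completers.

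The adjusted models could supply the strata, but their wording leaves two gaps. Gender is an example, so nothing obliges the analyst to include it. Site is explained by the place of intervention delivery, and waitlist participants are offered the intervention only after their week-16 assessment. The plan does not say that the site used in the models is the site used at randomization, nor how it is coded for the waitlist arm.

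**Working it through.** **1. The plan's own figure.** Inputs (Section 13): 22 per arm, effect size 0.80, independent-samples t-test. Alpha is not stated for this calculation; two-sided 0.05 is assumed. The noncentrality is 0.80 / sqrt(1/22 + 1/22) = 2.65 on 42 degrees of freedom. Exact power is 73.6% (normal approximation 75.6%); one-sided 0.05 gives 83.3%. The stated 80% is not reproduced under either. That is a separate matter, but it means the unadjusted baseline below is about 74% to 77%, not 80%.

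**2. Why the unadjusted test can be conservative.** Let R2 be the share of outcome variance explained by site and gender, with total variance 1. Under perfect balance within strata the arm difference has variance (1 - R2)(1/n1 + 1/n2), while the t-test estimates about (1/n1 + 1/n2). True size is then about P(|Z| > 1.96 / sqrt(1 - R2)):
- R2 = 0.10: 1.96/0.949 = 2.07, giving 3.9%
- R2 = 0.20: 1.96/0.894 = 2.19, giving 2.8%
- R2 = 0.30: 1.96/0.837 = 2.34, giving 1.9%

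Incomplete blocks and dropout weaken the balance, so the real figures lie between these and 5%.

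**3. Simulated size of the unadjusted t-test.** 60 randomized, 44 analysed, dropout at random, 8,000 trials per cell. Six or eight strata were tried, because Section 6 speaks of four study locations and Table 2 in Section 9 of three sites. R2 and block size are assumptions.

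| R2 | Blocks of 4 within strata | Simple randomization |
|---|---|---|
| 0 | 5.0-5.1% | 5.0-5.3% |
| 0.10 | 4.2% | 4.6-5.2% |
| 0.20 | 3.5-3.7% | 4.8-5.0% |
| 0.30 | 2.9-3.0% | 4.9% |

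Without balance within strata the test keeps its nominal size.

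**4. Power at 0.80, adjusted against unadjusted.** The adjusted model is outcome on arm + gender + site. 60 randomized, 45 completers, two-sided 5%, 6,000 trials per cell.

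| R2 | Blocked, 4 sites | Blocked, 3 sites | Unblocked, 4 sites |
|---|---|---|---|
| 0 | 72% vs 74% | 73% vs 74% | 69% vs 73% |
| 0.10 | 78% vs 76% | 77% vs 75% | equal |
| 0.20 | 81% vs 75% | 81% vs 75% | 78% vs 73% |
| 0.30 | 86% vs 76% | 87% vs 77% | 84% vs 74% |

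Across this and a second simulation of the same additive model, the change is about +3 to +11 points at R2 of 0.20-0.30, 0 to +3 at 0.10, and -1 to -5 at 0.

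**5. Sensitivity to the form of adjustment.** A separate indicator for every site-by-gender cell uses 5 or 7 degrees of freedom instead of 3 or 4, and does less well. With eight strata and no blocking, it gives 67.9% vs 72.2% at R2 = 0.10 and 73.8% vs 72.6% at 0.20. The additive form is therefore the one to specify.

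**The case against.** A reader might infer that the strata are missing from every week-12 and week-16 comparison, and that the planned tests are therefore too conservative and underpowered. The documents do not support that, for four reasons.

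- **The models do mention the strata.** Model 3 compares the arms on PCL-5 at each time point, so at weeks 12 and 16, and allows for participant characteristics and within-site correlation. Models 1 and 2 list study site and give gender as an example. Only the tests labelled unadjusted omit both.
- **Waitlist participants do have a site.** Randomization is within site, so each participant has one before allocation. The delivery-based wording is ambiguous; nothing shows that site would be missing or miscoded for controls. Nor has any conservatism of Models 1-3 been shown: the size calculation concerns the t-test alone.
- **Conservatism needs balance within strata.** The plan states no blocking, and under simple randomization the t-test keeps its size.
- **A gain in power needs prognostic strata.** The sex-specific binge cut-offs concern one of three alcohol variables, and a lower threshold for women could reduce a gender difference as easily as reflect one. Nothing is offered for site or for PCL-5.

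It can be added that this is a feasibility pilot, that the plan expects more power from the mixed models than from the t-test, and that a valid, perhaps slightly conservative first test does limited harm.

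All of this stands, and it makes both consequences conditional. It does not remove the mismatch: the comparison stated first, and the only one with a power figure, ignores the factors used to randomize. For alcohol, Models 1 and 2 estimate contrasts between periods and time trends rather than a week-12 comparison. In no model is gender a committed term or site defined as site at randomization.

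**Conclusion.** The point holds in conditional form. The initial week-12 and week-16 tests omit both randomization factors, and Models 1-3 do not clearly commit to those factors for both arms.

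- **Size.** If allocation is balanced within strata and the strata are prognostic, the unadjusted t-test's type I error is about 4% at R2 of 0.10-0.20 and about 3% at 0.30. Otherwise it is near 5%.
- **Power at 0.80.** With or without blocking, additive adjustment for gender and site gains about 3 to 11 points at R2 of 0.20-0.30, is neutral to slightly positive at 0.10, and costs about 1 to 5 points at 0.

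These figures rest on an assumed R2, blocks of 4 where blocking is assumed, dropout at random, and two-sided 0.05. The documents give none of these. The change is a cheap improvement, not the repair of an invalid analysis.

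**What to change.** **Section 13, preliminary clinical outcomes.** Make the week-12 and week-16 arm comparison a linear model of the outcome on arm, gender and site at randomization, with site recorded for both arms. Where a rank test is needed, use the van Elteren test stratified by the same factors. The unadjusted test may stay as a descriptive supplement.

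**Section 13, Models 1-3.** Name gender and site at randomization as terms for both arms, and define the site indicator as the randomization site instead of the place of delivery.

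**Section 11.** State whether allocation is blocked within strata, and reconcile four study locations (Section 6) with three sites (Table 2, Section 9), since this fixes the number of strata at eight or six.

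**Cost.** Plan wording and one recorded variable. The linear model spends three degrees of freedom with three sites (1 for gender + 2 for site) or four with four sites (1 + 3), with the small power loss given above if neither factor predicts outcome. With 45 completers there are about 45/8 = 5.6 to 45/6 = 7.5 per stratum, so in the van Elteren test a stratum left with only one arm contributes nothing.

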## INVESTIGATOR STUDY PLAN - REQUIRED

*administer a client satisfaction measure that will unblind the Co-I to which subjects are in the waitlist control group.)*

**Intervention:** Participants randomized to receive the intervention will be provided weekly individual treatment with one of four ASL-fluent study clinicians, based on preferred location and transportation needs. Each participant in this condition will receive 12 one-hour sessions of treatment. The maximum length of treatment will be capped at six months and the total number of completed sessions will be tracked as a measure of participant adherence. Therapists will treat an approximately equal percentage of participants, in order to minimize confounding of therapist effect and study site on treatment outcome.

Treatment sessions will be provided in each study clinician's private practice office, in direct response to findings from the PI's NIDCD R21, which revealed Deaf people's communal fear of academic research settings due to a long history of mistreatment by doctors and biomedical researchers (e.g., eugenics) (Anderson, Wolf Craig, & Ziedonis, 2016; Anderson et al., 2018; Anderson, Wolf Craig, & Ziedonis, 2017; McKee, Schlehofer, & Thew, 2013; Lane, 2005). As such, study therapists must be independently licensed in MA and will take on professional liability for the cases that they see. Study therapists will be compensated \$80 a session – a rate that is comparable to the average insurance reimbursement for individual therapy sessions with Deaf clients. Proof of sufficient liability insurance will be obtained from each study therapist prior to beginning the RCT.

**Waitlist Control:** Following the final assessment at 16 weeks, waitlist control participants will be offered the opportunity to receive the 12-session *Seeking Safety + Signs of Safety* protocol. This 16 week waiting period is equivalent to the current waitlist to receive psychotherapy services through the PI's outpatient clinic. Participants who are randomized to the waitlist, but express immediate need for services during the waitlist period will be provided referral to non-study treatment options (i.e., supportive psychotherapy provided either directly in ASL or with an ASL interpreter) and subsequently coded as a non-retained waitlist participant.

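### The stated 80% power is about 74% for the plan's own t-test, and neither that figure nor the initial week-12 and week-16 tests allow for the four-clinician clustering that Model 3 accepts

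*Combined protocol and SAP*

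**What the plan says.** Section 11 (Study Conditions) randomizes individuals within site, stratified by gender. Under Intervention, the experimental arm receives "weekly individual treatment with one of four ASL-fluent study clinicians", with caseloads kept roughly equal. Waitlist participants are offered the protocol only after the week-16 assessment, so they have no study clinician during the comparison.

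Section 13 opens the clinical analysis with unadjusted comparisons at weeks 12 and 16, which "will use a standard t-test (or Wilcoxon non-parametric test, depending on the outcome distribution"). Mixed models follow. Models 1 and 2 (alcohol) list clinician and site indicators among the predictors and allow for repeated measures "as well as correlation among participants receiving intervention in the same study site". Model 3 (PCL-5) is to adjust for "within-clinician, within-site, and repeated measures correlation".

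The sample size paragraph says that 22 completers per arm "will have 80% power to detect a large effect size (0.80) comparing two means using a two independent sample t-test". It gives no alpha, sidedness, ICC or design effect. It explains the choice of the t-test by how little is known about the inputs a mixed-model calculation needs, and then asserts that the mixed models will have more power because they partition the variance.

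**The concern.** There are two separate problems. The first is arithmetic: the 80% looks too high for the test it names, before any question of clustering.

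The second is structural. The trial is partially nested: four clusters in one arm and none in the other. Participants who share a clinician may have correlated outcomes, and the plan accepts this in Model 3. A t-test or Wilcoxon test treats them as independent. If the correlation is real, the standard error of the arm difference omits between-clinician variation, and a test that includes it has few degrees of freedom. At stake are the p-values and intervals at weeks 12 and 16, and what the sponsor believes this trial can detect when sizing the full trial, which may use other clinicians.

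**Working it through.** **Inputs from the plan.** 22 completers per arm and d = 0.80 (Section 13); 60 x 0.75 = 45 retained (Section 25); four clinicians with about equal caseloads (Section 11), so 22/4 = 5.5 treated completers each; PCL-5 SD 21.2 (Section 13).

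**Assumptions.** Two-sided 5%; clinician ICC from 0 to 0.15; total variance 1 in each arm. The plan gives neither alpha nor an ICC.

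**Step 1: the plan's own figure.** Under independence SE = sqrt(1/22 + 1/22) = 0.3015 and the noncentrality is 0.80/0.3015 = 2.653 on 42 df, with critical value 2.018. Exact power is 73.6% (75.6% by normal approximation; 74.6% with 22 versus 23). One-sided 5% gives 83.3%. Neither convention gives 80%. Two-sided, 80% needs 26 per arm, or d = 0.865 with 22 per arm. On the PCL-5 that is 0.865 x 21.2 = 18.3 points, against 0.80 x 21.2 = 17.0.

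**Step 2: clustering in the treated arm.** The design effect is 1 + (5.5 - 1) x ICC, applied to the treated arm only. At ICC 0.05 it is 1.225. Then SE = sqrt(1.225/22 + 1/22) = 0.3180, which is 1.055 times the SE assumed under independence. A matching test takes the treated-arm variance from four clinicians (3 df) and the control variance from 21 df. With v_t = 1.225/22 = 0.0557 and v_c = 1/22 = 0.0455, Satterthwaite df = (v_t + v_c)^2 / (v_t^2/3 + v_c^2/21) = 9.0. False-positive rates and the last column are simulated (60,000 replicates, caseloads 6/6/5/5).

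| ICC | Design effect | True SE / independence SE | t-test false positives | Satterthwaite df | Clustered power, formula | Clustered power, simulated |
|---|---|---|---|---|---|---|
| 0 | 1.000 | 1.000 | 4.8% | 10.5 | 67.2% | 66.2% |
| 0.02 | 1.090 | 1.022 | 5.6% | 9.8 | 64.7% | 63.5% |
| 0.05 | 1.225 | 1.055 | 6.4% | 9.0 | 61.2% | 60.5% |
| 0.10 | 1.450 | 1.107 | 7.6% | 8.0 | 55.8% | 55.8% |
| 0.15 | 1.675 | 1.157 | 9.1% | 7.3 | 51.2% | 51.5% |

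**Step 3: the offset from site.** Site is balanced across arms by the randomization but left out of the t-test, which makes the test conservative where sites differ equally in both arms. With a site ICC of 0.10 and no clinician effect, simulated false positives are 4.1%. Adding a clinician ICC of 0.05 brings them to 5.6%.

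**Step 4: splitting the gap at ICC 0.05.** From 80% to 73.6% (6.4 points) is the arithmetic in Step 1. From 73.9% (simulated t-test, ICC 0) to 66.2% (7.7 points) is the cost of having four clusters. From 66.2% to 60.5% (5.7 points) is the assumed correlation.

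**Step 5: the form of the clinician term.** Write the term as u_j, constant over visits. In change from baseline, (… + u_j at week 12) - (… + u_j at baseline), it cancels. The arm effects in Models 1 and 3 are arm-by-period and arm-by-visit contrasts, so a constant intercept would leave their standard errors without an allowance for clinician effects that begin only once treatment starts. Section 13 does not say which form is meant.

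**The case against.** The t-tests are labelled initial and unadjusted, and the plan goes straight on to models that carry site and clinician terms. A reader might infer that the t-tests are the lead analysis or that the plan overlooks clustering; Section 13 supports neither. A reader might also infer that Models 1 to 3 fail to handle it. That does not follow, because the form of the clinician term is not stated, and the wording on participants receiving the intervention at the same site can be read as treated-arm clustering. What stands is that the form needs to be specified.

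It is also tempting to say outright that the error bars are too narrow. That requires a positive ICC, which the documents do not give, and inference beyond these four clinicians. At ICC 0.05 the effect is small, and site works against it.

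The remedy has limits. With four clusters the clinician variance is poorly estimated: in simulation at ICC 0.05, a version truncated at zero estimated it as zero in about 50% of trials and rejected a true null 4.1% of the time, so it is somewhat conservative. Finally, this is a feasibility pilot. The plan warns that its models may be optimistic, and says that its sample size reflects limited scope. That lowers the stakes but does not make the 80% correct.

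**Conclusion.** The point holds in two parts of different strength. The power figure is wrong as written: about 74%, not 80%, at two-sided 5%. This needs no ICC, only the assumed alpha, and one-sided 5% does not rescue it (83%).

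The clustering part is conditional. For clinician ICCs of 0.02 to 0.15, and inference beyond these clinicians, the t-test rejects a true null about 5.5% to 9% of the time before any site offset. A clinician-clustered comparison has about 64% to 51% power over that range. Its roughly 66% at ICC zero does not depend on the ICC, only on treating four clinicians as random clusters. A reader might infer that clustering explains the whole drop from 80% to about 60%; roughly a third of it is the arithmetic error alone.

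The claim that the mixed models will have more power is unsafe as stated. Repeated measures may help, but four clusters can reverse the gain. This should be corrected; it does not undermine the trial's feasibility aims.

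**What to change.** In Section 13:

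1. State alpha and sidedness. Restate power as about 74% for the independent t-test (two-sided 5%, 22 per arm, d = 0.80). Then show about 51% to 66% for a clinician-clustered comparison over an assumed ICC range of 0.15 to 0, as a range rather than one headline value. Remove the unqualified statement that the mixed models will have more power.
2. Label the plain t-test and Wilcoxon comparisons descriptive. Base week-12 and week-16 inference on the mixed models, with the clinician effect specified for the experimental arm after baseline only, not solely as a time-constant intercept. Use Satterthwaite or Kenward-Roger degrees of freedom, and keep site and gender in the model as randomization strata. Section 6 lists four study locations while Table 2 counts three sites, so state whether site and clinician coincide. The power range above leaves site out and could be lower if they do.
3. Report the clinician variance with its interval, for planning the full trial.

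The cost is SAP wording and a few lines of PROC MIXED code, with no new data or participants. The downsides are wider intervals, a less favourable stated power, and a clinician variance that will often be estimated at zero.
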